## **Change #58**

### 9.2 Immunogenicity

Immunogenicity will be assessed through listing of individual results by subject and summary tables. Immunogenicity data will be correlated with PK and efficacy readout. In addition, immunogenicity will be correlated with possible safety findings.

A cut point will be determined by the bioanalytical laboratory during assay validation. This cutpoint will be used to determine the status of ADAb in the test sample as above the cut point (ACP) or below the cut point (BCP). For any ADAb test samples with results that are ACP, a further confirmatory assay will be performed, the results of which will be determined as either 'confirmed positive' (CP) or 'not confirmed positive' (NCP).

The following definitions will be applied regarding classification of test samples:.

- An ADAb status will be confirmed as positive for any sample with an ADAb level that is ACP and CP.
- An ADAb status of negative will be concluded for any sample with an ADAb level that is either BCP or ACP and NCP.

Confirmed positive samples will be titrated. The dilution factor will be reported. The titer represents the last dilution factor of the sample's titration series still scoring positive in the

screening ADAb assay. Subjects will receive an overall classification, inclusive of Baseline and Post-Baseline results, and be classified as follows based on the ADAb assay results:.

- ADAb negative: no confirmed positive ADAb samples at any of the sampling time points.
- ADAb positive: confirmed positive ADAb samples at one or more sampling time points.

Summaries will be done separately in Part A by axSpA subpopulation and overall using PKSA and in Part B by treatment group using PKSB. Part B summary will not include post-flare assessments. Separate summary by treatment group will be produced for subjects who flare in Part B and start escape therapy including only the post-flare assessments.

### **Has been changed to:**

Immunogenicity will be assessed through listing of individual results by subject and summary tables. Immunogenicity data will be correlated with PK and efficacy readout.

A cut point will be determined by the bioanalytical laboratory during assay validation. This cut point will be used to determine the status of ADAb in the test sample.

The following definitions will be applied regarding classification of test samples:

- An ADAb status will be confirmed as positive for any sample with an ADAb level that is positive screen and positive immunodepletion.
- An ADAb status of negative will be concluded for any sample with an ADAb level that is either negative screen or positive screen and negative immunodepletion.

Confirmed positive samples will be titrated. The dilution factor will be reported. The titer represents the last dilution factor of the sample's titration series still scoring positive in the screening ADAb assay. ADAb titer dilution factor is presented in the listings and summaries excluding the minimum required dilution (MRD), i.e. reportable values are divided by 100.

If the titer for an ADAb level that is positive screen and positive immunodepletion is missing, then a conservative will be used and ADAb status will be consider as positive. No imputation rules apply for the missing titer.

If the ADAb level is positive screen but no confirmatory result could be determined, then then a conservative will be used and ADAb status will be consider as positive.

Anomalous value will be not included in summaries/analysis and will be reviewed and flagged by pharmacokineticist.

Subjects will have the following Baseline ADAb status:

Baseline ADAb Status positive is defined as having an ADAb confirmed positive inhibition result at baseline, Baseline ADAb Status negative is defined as having negative inhibition result at baseline.

Subjects will receive a treatment-emergent ADAb status, inclusive of Baseline and Post-Baseline results (including SFU), and be classified as follows based on the ADAb assay results:

- TE ADAb status positive is defined as either (i) baseline ADAb negative subjects having at least one ADAb confirmed positive sample post baseline or ii) baseline ADAb positive subjects with at least one post baseline sample with  $\geq$ minimum significant ratio (MSR) -fold

increase from baseline on CZP treatment. The MSR will be defined during the process of sample analysis and is disease-specific.

- TE ADAb status negative is defined as having no samples either ADAb positive or with values  $\geq$ MSR -fold increase from baseline.

Once determined positive, the highest titer during Part A and Part B (including Escape and SFU) is used to categorize the subject.

- Positive  $<512$ ,
- Positive  $512- \leq 1024$ ,
- Positive  $>1024$ .

In addition, for some outputs also the subjects with TE ADAb status negative will be presented.

The TE ADAb will be also defined for the different treatment periods. For each Period the SFU visit will be considered:

- Part A TE ADAb status positive is defined as either (i) baseline ADAb negative subjects having at least one ADAb confirmed positive sample post baseline during Part A or ii) baseline ADAb positive subjects with at least one post baseline sample with  $\geq$ MSR increase from baseline on CZP treatment during Part A. Once determined positive, the highest titer during Part A is used to categorize the subject.
- Part A TE ADAb status negative is defined as having no samples either ADAb positive or with values  $\geq$ MSR increase from baseline during Part A.
- Part B TE ADAb Status positive is defined as either (i) baseline ADAb negative subjects having at least one ADAb confirmed positive sample post baseline during Part B or ii) baseline ADAb positive subjects with at least one post baseline sample with  $\geq$ MSR increase from baseline on CZP treatment during Part B. Once determined positive, only the highest titer during Part is used to categorize the subject. For subjects with flare in Part B, any assessments after Escape treatment are not included.
- Part B TE ADAb Status negative is defined as having no samples either ADAb positive or with values  $\geq$ MSR increase from baseline during Part B (excluding any values up to 8 weeks post first Part B dose).
- Escape TE ADAb Status positive is defined as either (i) baseline ADAb negative subjects having at least one ADAb confirmed positive sample post baseline during Escape Part or ii) baseline ADAb positive subjects with at least one post baseline sample with  $\geq$ MSR increase from baseline on CZP treatment during Escape Part B. Once determined positive, only the highest titer during Escape is used to categorize the subject.
- Escape TE ADAb Status negative is defined as having no samples either ADAb positive or with values  $\geq$ MSR increase from baseline during Escape Part. Once determined positive, only the highest titer during Escape is used to categorize the subject.

Summaries will be done using PKSB.

Summary of shift from Baseline ADAb status with titer classification to TE ADAb Status with titer classification by treatment group and for all subjects will be presented during the entire study.

The shift table will be repeated for

- Part A TE ADAb status with titer classification to Part B TE ADAb status with titer classification by treatment group and for all subjects during Part B.
- Part B TE ADAb status with Part B titer classification to Escape Part TE ADAb status with Escape titer classification by treatment group and for all subjects during Escape Part.

The time to achieving TE ADAb for all subjects will be analyzed based on Kaplan-Meier methods. Subjects will be considered to have an event at the time where treatment-emergent ADAb positive is first achieved during treatment period excluding Baseline/pre-treatment. Subjects classified as treatment-emergent ADAb negative will be censored at the time of last available ADAb result. The median and 95% CI based on the Kaplan-Meier estimation will also be presented. A plot of time to first ADAb positivity will be presented.

Number and percentage of subjects with ADAb titer above the specified cut point (“categorized”) at any visit during the treatment period, separated by treatment group will be presented.

A summary of flare responder during Part B (NRI) and ASDAS MI responder at Week 96 (NRI) by treatment group and by highest ADAb titer (“categorized”) per subject will be presented during Part A and Part B (excluding Escape). This table will be repeated for Part B (excluding Escape).

A scatter plot of CZP Plasma Concentration and ADAb titer during Part A for all subjects will be presented. The scatter plot will be repeated for Part B by treatment group.

Spaghetti plots of ADAb titer on a loglog scale by week from CZP first dosing separated by treatment group and TE ADAb status/titer classification will be presented for subjects with flare and no flare per NRI approach.

All individual ADAb results will be listed at subject level.

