### **3.2.22 Flare**

A subject is considered to have experienced a flare if a subject has an ASDAS  $\geq 2.1$  at 2 consecutive visits or an ASDAS  $>3.5$  at any visit during Part B up until Week 96.

If a subject has an intermittent missing ASDAS score (ie, a missing value at 1 visit but non-missing values at the previous and subsequent visit), then the missing value will be ignored and the occurrence of a flare will be based on the 2 available values.

If the ASDAS score is missing at 2 or more consecutive visits, then the subject will be considered to have experienced a flare (even if ASDAS scores are available after the missed visits).

There is also the possibility to report one unscheduled ASDAS between two scheduled ASDAS assessments. The same rules as for the scheduled ASDAS apply for the unscheduled ASDAS.

The unscheduled ASDAS will be taken into account for flare calculation for two consecutive visits if there are more than 13 calendar days between two consecutive ASDAS calculated dates.

If the ASDAS score is missing at 2 scheduled visits and unscheduled ASDAS entry present in between and not larger than 3.5, then the subject will not be considered to have experienced a flare.

Occurrence of a flare will be based solely on the observed ASDAS values and will not take into account any imputation of ASDAS. Occurrence of a flare will be determined based on the actual

data entered into the eCRF for the individual ASDAS components, not based on data from the interactive voice or web response system (IXRS).

If a subject prematurely withdraws from Part B at any point for any reason, then the subject will be considered to have experienced a flare.

If a subject was incorrectly identified as flared at any point in Part B due to late data entry in IXRS and went to escape Part B, then the subject will be considered to have experienced a flare.

Sensitivity analyses will be conducted using different approaches for definition of flare. These approaches are described hereafter.

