- TE ADAb status negative is defined as having no samples either ADAb positive or with values  $\geq$ MSR -fold increase from baseline.

Once determined positive, the highest titer during Part A and Part B (including Escape and SFU) is used to categorize the subject.

- Positive  $<512$ ,
- Positive  $512- \leq 1024$ ,
- Positive  $>1024$ .

In addition, for some outputs also the subjects with TE ADAb status negative will be presented.

The TE ADAb will be also defined for the different treatment periods. For each Period the SFU visit will be considered:

- Part A TE ADAb status positive is defined as either (i) baseline ADAb negative subjects having at least one ADAb confirmed positive sample post baseline during Part A or ii) baseline ADAb positive subjects with at least one post baseline sample with  $\geq$ MSR increase from baseline on CZP treatment during Part A. Once determined positive, the highest titer during Part A is used to categorize the subject.
- Part A TE ADAb status negative is defined as having no samples either ADAb positive or with values  $\geq$ MSR increase from baseline during Part A.
- Part B TE ADAb Status positive is defined as either (i) baseline ADAb negative subjects having at least one ADAb confirmed positive sample post baseline during Part B or ii) baseline ADAb positive subjects with at least one post baseline sample with  $\geq$ MSR increase from baseline on CZP treatment during Part B. Once determined positive, only the highest titer during Part is used to categorize the subject. For subjects with flare in Part B, any assessments after Escape treatment are not included.
- Part B TE ADAb Status negative is defined as having no samples either ADAb positive or with values  $\geq$ MSR increase from baseline during Part B (excluding any values up to 8 weeks post first Part B dose).
- Escape TE ADAb Status positive is defined as either (i) baseline ADAb negative subjects having at least one ADAb confirmed positive sample post baseline during Escape Part or ii) baseline ADAb positive subjects with at least one post baseline sample with  $\geq$ MSR increase from baseline on CZP treatment during Escape Part B. Once determined positive, only the highest titer during Escape is used to categorize the subject.

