- Escape TE ADAb Status negative is defined as having no samples either ADAb positive or with values  $\geq$ MSR increase from baseline during Escape Part. Once determined positive, only the highest titer during Escape is used to categorize the subject.

Summaries will be done using PKSB.

Summary of shift from Baseline ADAb status with titer classification to TE ADAb Status with titer classification by treatment group and for all subjects will be presented during the entire study.

The shift table will be repeated for

- Part A TE ADAb status with titer classification to Part B TE ADAb status with titer classification by treatment group and for all subjects during Part B.
- Part B TE ADAb status with Part B titer classification to Escape Part TE ADAb status with Escape titer classification by treatment group and for all subjects during Escape Part.

The time to achieving TE ADAb for all subjects will be analyzed based on Kaplan-Meier methods. Subjects will be considered to have an event at the time where treatment-emergent ADAb positive is first achieved during treatment period excluding Baseline/pre-treatment. Subjects classified as treatment-emergent ADAb negative will be censored at the time of last available ADAb result. The median and 95% CI based on the Kaplan-Meier estimation will also be presented. A plot of time to first ADAb positivity will be presented.

Number and percentage of subjects with ADAb titer above the specified cut point (“categorized”) at any visit during the treatment period, separated by treatment group will be presented.

A summary of flare responder during Part B (NRI) and ASDAS MI responder at Week 96 (NRI) by treatment group and by highest ADAb titer (“categorized”) per subject will be presented during Part A and Part B (excluding Escape). This table will be repeated for Part B (excluding Escape).

A scatter plot of CZP Plasma Concentration and ADAb titer during Part A for all subjects will be presented. The scatter plot will be repeated for Part B by treatment group.

Spaghetti plots of ADAb titer on a loglog scale by week from CZP first dosing separated by treatment group and TE ADAb status/titer classification will be presented for subjects with flare and no flare per NRI approach.

All individual ADAb results will be listed at subject level.

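### The flare and ASDAS-MI tables by highest ADAb titre take the maximum over a window whose length depends on the outcome, which biases them toward showing no harm from high titres

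*SAP*

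**What the plan says.** Section 9.2 (current text, repeated in the log of SAP Amendment 2, Change #58) tabulates two outcomes by each subject's highest titre: a "summary of flare responder during Part B (NRI) and ASDAS MI responder at Week 96 (NRI) by treatment group and by highest ADAb titer". The outcomes are flare during Part B and ASDAS-MI at Week 96, both with non-responder imputation (NRI). The window is given as "per subject will be presented during Part A and Part B (excluding Escape). This table will be repeated for Part B (excluding Escape".

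The period definitions in the same section bear on that window:
- For the Part B status, "For subjects with flare in Part B, any assessments after Escape treatment are not included".
- "For each Period the SFU visit will be considered", although the table's own sentence does not name the SFU.
- The Part B negative definition alone carries a further exclusion ("excluding any values up to 8 weeks post first Part B dose"). Nothing says whether it applies to the highest titre.
- The overall status uses a different window: "the highest titer during Part A and Part B (including Escape and SFU) is used to categorize the subject".

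On the outcome side, Section 2.3.3 places Escape Week 0 two weeks after the flare-defining assessment, or earlier. Section 4.2 counts data missing because escape has started as non-response, so escaped subjects are ASDAS-MI non-responders by rule. Section 3.2.22 also counts withdrawals as flares: "If a subject prematurely withdraws from Part B at any point for any reason".

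**The concern.** The row a subject falls into is a maximum over samples, and the outcome in the columns decides how long sampling continues. A subject who flares and escapes stops contributing titres at about Escape Week 0. A subject who never flares contributes up to Week 96, and perhaps to the SFU. This is the immortal-time problem in another form: staying flare-free gives more time to record a high titre.

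Leaving Escape samples out keeps post-outcome titres away from the escapers, but it is also what makes the windows unequal. For this table, Section 9.2 states no Part B Baseline titre, landmark, time-dependent titre or allowance for window length. The same section says immunogenicity will be correlated with efficacy, and these tables are part of that. A reader could take them as evidence that high titres are harmless, or even go with better maintenance of response.

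**Working it through.** **1. Inputs from the SAP.** Flare-free rates are 80% (Q2W), 75% (Q4W) and 45% (PBO), with 70 per arm (Section 2.4). Part B lasts 48 weeks. Escape starts 2 weeks after flare. The last double-blind dose is at Week 94 and the SFU is 10 weeks later, at Week 104 (Sections 2.3.3 and 2.3.4). The disputed tables have no stated figure of their own. As a check on the rates, the stated power of 98% and 94% is reproduced closely: a continuity-corrected z test gives 98.9% and 94.1%, and Fisher's exact test 98.9% and 94.0%.

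**2. Window lengths.** With constant hazard λ = −ln(S)/48, the mean flare week among those who flare is 1/λ − 48·S/(1 − S). Adding 2 weeks gives Escape Week 0.

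| Arm | S | Mean flare week | Part B window to escape | Share of 48 (of 56 with SFU) |
|---|---|---|---|---|
| PBO | 0.45 | 60.11 − 39.27 = 20.8 | 22.8 | 48% (41%) |
| Q4W | 0.75 | 166.85 − 144 = 22.9 | 24.9 | 52% (44%) |
| Q2W | 0.80 | 215.11 − 192 = 23.1 | 25.1 | 52% (45%) |

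With Part A's common 48 weeks added, the share rises to 74–76% (68–70% with SFU).

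**3. Spurious gap when titre and flare are unrelated (PBO).** Assumptions not in the SAP: high titres persist, and onset has rate h per week. P(high) is 1 − exp(−h × weeks observed).
- *h = 0.003 throughout, Escape Week 0 and SFU samples counted.* Flare-free: 1 − exp(−0.312) = 0.268. Flared, averaged over flare times: 0.191. Flare-free rate in the high row: 0.45×0.268/(0.45×0.268 + 0.55×0.191) = 53%. In the other row: 0.45×0.732/(0.45×0.732 + 0.55×0.809) = 43%. The gap is about 11 points before rounding.
- *Low end: h = 0.003 in Part A and 0.001 in Part B, Escape Week 0 counted, SFU not.* P(high) is 0.175 against 0.154, giving 48% against 44%, about 4 points. With persistent titres and an Escape Week 0 sample the two tables coincide, so this applies to both.
- *High end: h = 0.003, samples at Weeks 60, 72, 84, 96 and SFU, none at Escape Week 0 (simulation, 600,000 subjects).* The Part B table shows 61% against 41% (20 points) and the Part A plus Part B table 56% against 42% (about 13). About 28% of flared PBO subjects then have no Part B sample and are counted here as not high. This is why the Part B table is the worse one.
- *Classing by titre at Week 48:* 45% against 45%, no gap.

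**4. True harm (PBO, flare hazard doubled after high titre, h = 0.003, overall flare-free rate held at 45%, SFU counted).**

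| Classification | High | Other |
|---|---|---|
| Part B, no Escape Week 0 sample | 46% | 45% |
| Part B, with Escape Week 0 sample | 37% | 47% |
| Part A + Part B | 37–39% | 47% |
| Up to Week 48 | 25% | 48% |

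**5. Wider grid.** Assumed: 5/20/40% high by Week 48, 2/10/30% newly high in Part B, PBO and Q2W, persistent titres. At hazard ratio 1 the SAP's windows give crude flare odds ratios of 0.41–0.97; Week 48 status gives 0.98–1.03. At hazard ratio 2 the ranges are 0.88–2.68 and 1.85–3.15. Over the 54 scenarios with hazard ratio 1.5, 2 or 3, the SAP's odds ratio is lower than the Week 48 one in all 54 and below 1 in 9. Some of that difference is expected, because late-onset subjects spend little time at raised risk. The hazard-ratio-1 results isolate the bias.

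**The case against.** A reader might infer that these tables will hide or reverse a harmful antibody effect. The documents do not support that as a certainty. The SAP gives no ADAb incidence and leaves the sampling schedule to the protocol. Reversal needs many new high titres in Part B or a weak effect; where most high titres arise in Part A, attenuation is small (Q2W at hazard ratio 2: odds ratio 2.06 against 2.11–2.19). The masked result in step 4 depends on there being no Escape Week 0 sample, whereas Sections 3.3 and 4.2 treat that visit as a Part B assessment for other purposes. It also depends on counting subjects without a Part B sample as not high, and PKSB membership (Section 3.6.8) may exclude some of them.

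Three further limits stand:
- Including the SFU is inferred from the period definitions. Without it the contrast is still 48 weeks against 23 to 25.
- Stopping at escape describes escapers, not every NRI flare. Withdrawals also count as flared without escaping; their follow-up ends early too, apart from a possible SFU sample.
- The tables are descriptive, with no test stated, and are not the only link. Sections 4.7 and 8.1.2 summarize flare by ADAb status, and there are titre plots by flare status.

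The last point does not cure the problem. On the overall definition, that status counts Escape and SFU titres, taken after the outcome and, for escapers from PBO or half-dose, on changed treatment. Omitting a p-value does not remove a systematic bias.

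**Conclusion.** The concern holds in this form: the outcome sets the length of the window over which the maximum titre is taken, and both tables are thereby biased toward showing no harm. The effect is at least as large in the Part B table, and larger when early escapers lack a Part B sample. ASDAS-MI at Week 96 inherits the bias through NRI.

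Under no true link and assumed onset of 0.1 to 0.3% per week, the spurious flare-free gap on PBO is about 4–20 points (Part B) and about 4–13 points (Part A plus Part B). Masking or reversal of a true harm is possible in some scenarios but is not established. These sizes rest on constant flare hazard, the assumed incidence and persistence of titres, and the assumed samples. The direction did not change in any scenario run. The primary efficacy test is unaffected.

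**What to change.** Make the main version of both tables a classification by highest titre up to and including Week 48 (Part B Baseline). That window is common to all randomized subjects and precedes the outcome. Define it explicitly: Part A TE ADAb status is close but not identical, because baseline-positive subjects without the required fold increase are not TE positive, and the SFU sentence must not extend the window for randomized subjects.

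If the Part B-window table is kept, choose one of these:
- Use a landmark (for example Part B week 12 among subjects not yet flared, which gave odds ratios of 0.98–1.04 under no link) or a time-dependent titre.
- Label the table as depending on the outcome and not for inferring an antibody effect.

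In either case state whether Escape Week 0 and SFU samples count, whether the 8-week exclusion applies, and how subjects without a Part B sample are classed.

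The cost is SAP wording and one derived variable for descriptive tables. The downside is that antibodies first arising after Week 48, including those under half-dose or withdrawal, do not enter the main class. That is a reason to keep a properly constructed Part B version beside it, along with the listings and plots.
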